1.5 Risks and Benefits

• The benefits of methylene blue:

Methylene blue causes vasoconstriction by inhibiting nitric oxide synthase and preventing subsequent activation of guanylyl cyclase in smooth muscle cells. This reaction increases systemic blood pressure and decreases vasopressor requirements for patients with vasoplegic syndrome. In LT surgery patients, hemodynamic stability without the requirements of vasopressors may allow immediate extubation at the end of the surgery and bypass the intensive care unit in the postoperative period, allowing faster recovery and improving outcomes. Advocates for early extubation have argued that it may be beneficial for the new organ graft to limit the exposure to mechanical ventilation. Kaisers et al reported the deleterious effects of positive end expiratory pressure (PEEP) on liver graft hemodynamics.

• The risks of methylene blue:

Common side effects include hypertension, discoloration of skin, hyperhidrosis, nausea, dizziness, headache, pain in limb, and abnormal urine color, hypersensitivity, hemolytic anemia

Medications which may accumulate with methylene blue due to inhibition of cytochrome P450 isozymes: Alfentanil, cyclosporine, digoxin, fentanyl, phenytoin, sirolimus, tacrolimus, warfarin.

Methylene blue is contraindicated in patients with glucose-6-phosphate dehydrogenase (G6PD) deficiency as it can result in a hemolytic response in patients with G6PD deficiency. The intravascular hemolysis typically occurs two to five days after drug administration and is typically self-limited.

Methylene blue may cause serotonin syndrome when used in combination with serotonergic drugs such as Selective serotonin reuptake inhibitors (SSRIs), serotonin and norepinephrine reuptake inhibitors (SNRIs), and monoamine oxidase inhibitors (MAOIs).

- The benefits of hydroxocobalamin: IV hydroxocobalamin is currently approved for cyanide poison treatment. Its ability to bind and inhibit the 3 main gasotransmitters (nitric oxide, carbon monoxide, and hydrogen sulfide) contributing to vasoplegic syndrome has made it a new treatment for intraoperative vasoplegic syndrome. Unlike methylene blue, it does not have the same implications in serotonin syndrome. Similar to the benefits of methylene blue on treating vasoplegic syndrome, hydroxocobalamin may play a major role to allow hemodynamic stability and early extubation in this particular LT population.

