- The risks of hydroxocobalamin: Common side effects include increased blood pressure, erythema, rash, nausea, decreased lymphocyte count, headache, and abnormal red urine color.

2 Study Objectives

Primary Objective

To assess the efficacy of hydroxocobalamin as compared to methylene blue on improving hemodynamic stability as measured by SVR, systemic blood pressure, and amount of vasopressors administered.

Secondary Objective

The secondary end point will examine the patient outcomes in the postoperative period as measured by early tracheal extubation after surgery, length of hospital and intensive care unit stay, perioperative complications (stroke, myocardial infarction, and acute renal failure), graft function, and survival rate.

3 Study Design

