3.3 Duration of Participation

Intraoperatively during LT surgery

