3.5 Secondary Study Endpoints

The secondary endpoints of the study are the patient outcomes in the postoperative period and 30-day mortality rate.

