6.4 Visit 3 (Off Study)

• Review of medical record will continue until study participants are discharged from the hospital

	Schedule of Events				
Study Activity	Visit la	Visit 1b	Visit 2	Visit 3	
Hydroxocobalamine or Methylene Blue			X		
Initial review of informed consent	Х				
Capacity to consent		Х			
Informed consent		Х			
Review of Medical Record	Х	Х		Х	
Concomitant Medications		Х	Х		
Adverse event evaluation			Х	X	

7 Statistical Plan

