7.2 Statistical Methods

Descriptive Statistics

Continuous variables will be summarized using the sample mean, median, standard deviation, interquartile range, and range. Categorical variables will be summarized using number and percentage of patients

Handling of Missing Data

This is a prospective study and therefore we do not anticipate any missing data. In the event of any unexpected missing data, no attempt to impute this missing data will be made; missing data will simply be treated as missing in the statistical analysis.

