For this study, the study treatment follow-up period is defined as 90 minutes following the last administration of study treatment.

Preexisting Condition

A preexisting condition is one that is present at the start of the study. A preexisting condition should be recorded as an adverse event if the frequency, intensity, or the character of the condition worsens during the study period.

General Physical Examination Findings

At screening, any clinically significant abnormality should be recorded as a preexisting condition. At the end of the study, any new clinically significant findings/abnormalities that meet the definition of an adverse event must also be recorded and documented as an adverse event.

Post-study Adverse Event

All unresolved adverse events should be followed by the sponsor-investigator until the events are resolved, the subject is lost to follow-up, or the adverse event is otherwise explained. At the last scheduled visit, the sponsor-investigator should instruct each subject to report, to the sponsor-investigator, any subsequent event(s) that the subject, or the subject's personal physician, believes might reasonably be related to participation in this study.

Hospitalization, Prolonged Hospitalization or Surgery

Any adverse event that results in hospitalization or prolonged hospitalization should be documented and reported as a serious adverse event unless specifically instructed otherwise in this protocol. Any condition responsible for surgery should be documented as an adverse event if the condition meets the criteria for an adverse event.

Neither the condition, hospitalization, prolonged hospitalization, nor surgery are reported as an adverse event in the following circumstances:

• Hospitalization or prolonged hospitalization for therapy of the target disease of the study, unless it is a worsening or increase in frequency of hospital admissions as judged by the clinical investigator.

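### Complications and graft function are followed only to hospital discharge, so the observation window depends on length of stay, itself an outcome, and can bias recorded rates downward in an arm discharged sooner

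*Combined protocol and SAP*

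**What the plan says.** The secondary objective in section 2 lists, besides early extubation, "length of hospital and intensive care unit stay, perioperative complications (stroke, myocardial infarction, and acute renal failure), graft function, and survival rate". Section 3.5 restates this as "The secondary endpoints of the study are the patient outcomes in the postoperative period and 30-day mortality rate". Mortality is the only one of these outcomes with a stated time point.

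Section 6.4 says how long outcomes are looked for: "Review of medical record will continue until study participants are discharged from the hospital". The Schedule of Events agrees, placing the last record review at Visit 3 (Off Study).

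For analysis, section 7.2 says "Categorical variables will be summarized using number and percentage of patients". It gives no time window, person-time or time-to-event summary.

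**The concern.** Record review ends at discharge, which happens after randomisation and may be affected by treatment. A patient who goes home on day 7 has 7 days in which a stroke, infarction or renal failure can be recorded. A patient who goes home on day 14 has 14. If one drug shortens stay, its patients are observed for less time, and a crude percentage does not correct for that. Some of an apparent difference in complications could then be a difference in observation time.

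The protocol regards recovery time as something treatment can change: section 1.5 says haemodynamic stability may let patients "bypass the intensive care unit in the postoperative period, allowing faster recovery and improving outcomes". The study is also open label (5.7), so those deciding on discharge may know the assignment.

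A second consequence needs no difference between arms. A percentage over a window that is unstated and varies by patient is hard to interpret or reuse, and section 7.1 says the descriptive data are meant to support later work.

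**Working it through.** **Step 1. Does any other section give these outcomes a common window?**

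- Section 3.3 gives the duration of participation as "Intraoperatively during LT surgery", and the Study Summary gives less than 12 hours. Neither reaches the postoperative period.
- Section 8.1, under the Adverse Event Reporting Period: "the study treatment follow-up period is defined as 90 minutes following the last administration of study treatment". This is far shorter than a hospital stay.
- Section 8.1, under Post-study Adverse Event: "All unresolved adverse events should be followed by the sponsor-investigator until the events are resolved", or until loss to follow-up or another explanation. This follows known events. The accompanying request for later reports covers only events thought related to participation. Neither is a search for new complications in every patient.
- Section 3.5 fixes 30 days, for mortality only.

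None does, so the rule in 6.4 governs.

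**Step 2. Is there a plan figure to reproduce?** No. Section 7.1 says the information is insufficient for a sample-size calculation. The only figure is 10 + 10 = 20 patients.

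**Step 3. How large could the artefact be?** All inputs here are assumptions: the same true 30-day complication risk R = 30% in both arms, and discharge on day L = 7 in one arm and L = 14 in the other. The true difference is zero, so any recorded difference is artefact. Three timing models were used:

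- Constant hazard: h = −ln(1 − R)/30 = −ln(0.70)/30 = 0.01189 per day; recorded risk = 1 − exp(−hL).
- 80% of events by day 7 and the rest spread evenly to day 30: recorded risk = R × [0.8 + 0.2 × (L − 7)/23].
- Exponential onset with mean m days, truncated at day 30: recorded risk = R × (1 − exp(−L/m)) / (1 − exp(−30/m)).

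| Timing of events | Discharge day 7 | Discharge day 14 | Difference (points) | Ratio |
|---|---|---|---|---|
| Constant hazard | 8.0% | 15.3% | 7.3 | 0.52 |
| Mean onset 7 days | 19.2% | 26.3% | 7.1 | 0.73 |
| 80% by day 7 | 24.0% | 25.8% | 1.8 | 0.93 |
| Mean onset 2 days | 29.1% | 30.0% | 0.9 | 0.97 |
| Mean onset 1 day | 30.0% | 30.0% | 0.0 | 1.00 |

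The largest gap is about 0.7 of a patient per arm of 10.

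**Step 4. Wider assumptions.** With R from 10% to 50% and stays of 7 versus 10, 7 versus 14 and 10 versus 20 days, under the constant-hazard and exponential-onset models, the artefact runs from 0 to about 16 points. The maximum is at R = 50%, 10 versus 20 days, constant hazard: 20.6% versus 37.0%, or 1.6 patients per 10.

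**Step 5. Stay varying between patients.** A simulation used gamma-distributed planned stays with means of 7 and 14 days, R = 30%, and 5 extra days after a recorded complication. It gave 6.9% versus 13.9% with onset spread evenly over 30 days, 17.9% versus 24.5% with mean onset 7 days, and 27.5% versus 29.5% with mean onset 2 days. The pattern is the same.

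**Step 6. With a fixed 30-day window** and complete records, both arms record 30% under every model, whatever the stay.

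This arithmetic applies to the complications. Graft function is not defined in the documents and may be a measurement rather than an event. For it, the point is only that no assessment time is fixed.

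**The case against.** A reader might infer that the arm discharged sooner must show a lower complication rate, or is always favoured. The documents do not support that. Only the opportunity to record events is certainly shorter. With equal true risk the expected recorded rate is lower or equal, and the gap vanishes if events come early. Section 2 calls these complications perioperative, and section 1.1 links stroke, infarction and renal failure to prolonged hypotension from vasoplegia. Both suggest early onset, so the constant-hazard row probably fits this setting least well. This stands, and it is why the range starts at zero.

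A reader might also take section 1.5 as predicting different stays in the two arms. It does not. The sentence about recovery describes methylene blue, and the section then describes a similar benefit for hydroxocobalamin. The 7 versus 14 day contrast is purely illustrative.

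Causality also runs the other way: complications prolong stay, so some association between short stay and few complications would be real effect. This stands too.

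Finally, the pilot is descriptive and very small. With 30% risk and 10 per arm, the standard error of a difference is sqrt(2 × 0.30 × 0.70/10) = 0.205, about 20 points, well above an artefact of 0 to 7. The planning gaps named in 7.1 are SVR, blood pressure and vasopressor amount, not complication rates. It would therefore go too far to say that this flaw alone makes the percentages impossible to compare.

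These arguments limit the size of the problem. They do not supply the missing window, and the documents give no event timing that would justify taking the gap as zero.

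**Conclusion.** The point holds as a weakness in how secondary outcomes are collected and reported. The window for the complications and graft function is set by discharge, varies by patient, depends on another outcome, and is not corrected in the analysis. If stay differs between arms, recorded complication rates can be biased downward in the arm discharged sooner.

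The size cannot be determined from the documents. It is about 0 to 7 points for 7 versus 14 days at an assumed 30% risk, and near zero if events occur in the first days. Whether any bias arises depends on a between-arm difference in stay that the documents do not predict.

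Severity is low to moderate. The outcomes are secondary and descriptive, no test is planned, there are 10 patients per arm, and the primary haemodynamic endpoint is unaffected. The change is worthwhile mainly because it is cheap.

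**What to change.** - **Section 6.4 and the Schedule of Events:** extend record review to a fixed day after study drug for every treated patient, whether or not discharged. Day 30 matches the mortality endpoint in 3.5, which also has no stated collection step for patients discharged before then. A vital-status check alone would not repair the complication counts.
- **Sections 3.5 and 7.2:** count stroke, myocardial infarction and acute renal failure over that same window in both arms, and assess graft function at a fixed, stated time. Report how many patients in each arm had records for the full window.
- **Discharge-limited counts:** label any that are kept as in-hospital and show them beside length of stay. If no later look-up is made, this is the minimum change.
- **Section 3.3 and the Study Summary:** align the participation-duration statements with the longer record review.

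The cost is a few sentences and one later record look-up for about 20 patients, with no new visit or procedure. The downside is that events treated elsewhere after discharge may not appear in the hospital's record, which is why record availability should be reported by arm.

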7.1 Sample Size Determination

Per the biostatistician from the Mayo Division of Biomedical Statistics and Informatics, the existing information on the changes of SVR, blood pressure, and amount of administered vasopressors altered by either medication are not sufficient for sample size calculation. The primary aim of this pilot study will be to determine feasibility and to collect descriptive data that can be used in future to obtain statistical power.

7.2 Statistical Methods

Descriptive Statistics

Continuous variables will be summarized using the sample mean, median, standard deviation, interquartile range, and range. Categorical variables will be summarized using number and percentage of patients

Handling of Missing Data

This is a prospective study and therefore we do not anticipate any missing data. In the event of any unexpected missing data, no attempt to impute this missing data will be made; missing data will simply be treated as missing in the statistical analysis.

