3.1 General Description

This randomized, prospective, open label, pilot study will involve 20 LT patients with intraoperative vasoplegic syndrome. If vasoplegic syndrome is identified via SVR lower than 500 dynes-sec/cm⁻⁵, the patients will be randomized to receiving either IV methylene blue or hydroxocobalamin (10 patients in each group). The administration of assigned medication will only take place once during surgery if patient is exhibiting vasoplegia after the reperfusion of the new organ as demonstrated by SVR lower than 500 dynes-sec/cm⁻⁵ sustained for a period of more than 5 minutes despite the administration of vasopressors. The primary end point will examine the efficacy of the two medications on treating intraoperative vasoplegic syndrome. The SVR, blood pressure, and amount of administrations will be recorded.

[figure not shown]
If the patients still present with vasoplegic syndrome 30 minutes after receiving IV methylene blue or hydroxocobalamin during LT surgery, the vasoplegia treatment which the patients have not received in the operating room would be utilized as life-saving measures per standard of care practice. The patients will be excluded from the comparison study, but the data of frequency of failure to effectively treat vasoplegia via certain medication may be utilized in understanding the rate of failure to provide effective treatment.

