4.4 Early Withdrawal of Subjects

4.4.1 When and How to Withdraw Subjects

Patients are free to withdraw at any time and for whatever reason. No data will be collected for withdrawn subjects. Withdrawn subjects may be replaced during the accrual period. Prespecified reasons for discontinuing include, but are not limited to, the following:

- Patient Request: Patient decided that he/she did not want to continue (for any reason)
- Adverse Event: Patient experienced a related or unrelated event that would interfere with the study objectives/evaluation
- Treatment Failure: If in the Principal Investigator and/or Investigators' judgment, the patient's condition required another form of treatment
- Inclusion/Exclusion Discrepancy/Violation: Patient should not have been enrolled
- Noncompliance: Patient is not complying with the protocol requirements (i.e. visit schedule, dosing, regimen, etc.); a patient is to be withdrawn if he/she misses two consecutive visits
- Other: Any other reason

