7.3 Subject Population(s) for Analysis

Each participant who received the study drug will be included in the primary analysis regardless of study withdrawal for any reason. In the event of any study withdrawals, in secondary analysis we will examine the sensitivity of our results to the exclusion of patients who withdrew.

8 Safety and Adverse Events

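### Section 3.1 removes non-responders from the comparison while section 7.3 keeps every treated patient, and following section 3.1 would select on the outcome

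*Combined protocol and SAP*

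**What the plan says.** The primary objective in section 2 is comparative: "To assess the efficacy of hydroxocobalamin as compared to methylene blue on improving hemodynamic stability", measured by SVR, blood pressure and vasopressor amount. Section 3.1 randomizes 20 patients, 10 per arm. Section 7.2 provides per-variable summaries and counts only ("Continuous variables will be summarized using the sample mean, median, standard deviation, interquartile range, and range"), and section 7.1 says the data are meant to inform the power of a later study.

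Three places decide who is analysed:

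- **Section 3.1.** "If the patients still present with vasoplegic syndrome 30 minutes after receiving IV methylene blue or hydroxocobalamin during LT surgery", the other drug is given under standard of care, and then "The patients will be excluded from the comparison study". Their failure frequency is kept as something that may be used.
- **Section 4.4.1.** Treatment failure is a listed reason for discontinuing, if in the investigator's judgment the patient's "condition required another form of treatment". The same section says: "No data will be collected for withdrawn subjects. Withdrawn subjects may be replaced during the accrual period".
- **Section 7.3.** "Each participant who received the study drug will be included in the primary analysis regardless of study withdrawal for any reason". It adds that "in secondary analysis we will examine the sensitivity of our results to the exclusion of patients who withdrew".

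**The concern.** A patient who is still vasoplegic at 30 minutes and receives the second drug is out of the comparison under section 3.1 and in the primary analysis under section 7.3. If the investigator also withdraws that patient for treatment failure, section 4.4.1 allows a replacement. Nothing says which rule prevails. In an open-label study the choice could be made after the results are known.

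The exclusion rule is also wrong in itself, because persistence of vasoplegia is the outcome. Entry requires SVR below 500 (section 4.1), and section 3.1 identifies the syndrome by the same threshold. If persistence is judged that way, every patient left in the comparison has an SVR that has risen to the threshold or above, whatever the drug did. When failure rates differ, the arm with more failures loses more of its poor results, and the difference between arms shrinks.

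The pilot's own purpose is at stake: a responder-only difference and SD would mislead the future power calculation.

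**Working it through.** Section 7.1 states that no sample size calculation was possible, so there is no planned figure to reproduce. The check is how far the exclusion rule could distort the comparison.

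**Inputs from the protocol.** 10 per arm (section 3.1). Methylene blue ineffective in 9 of 14 = 64.3% (section 1.3), exact 95% CI 35.1% to 87.2%.

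**Assumptions not in the protocol.** 30-minute SVR is Normal with the same SD in both arms; failure means SVR still below one shared threshold; hydroxocobalamin failure p is 20%, 30% or 50%. The 9/14 comes from a retrospective series that defined ineffectiveness by haemodynamics or vasopressor need, not by the 30-minute rule.

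**Patients lost.** 10 × 9/14 = 6.4 methylene blue patients would leave the comparison and 3.6 would stay (6.5 to 1.3 stay over the exact interval).

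**Responder-only difference.** In SD units, with z = Φ⁻¹(p):

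- true difference = z(9/14) − z(p), with z(9/14) = 0.366;
- upward shift of the responder mean: λ = φ(z)/(1 − p);
- responder SD = √(1 + zλ − λ²);
- responder-only difference = true difference + λ(p) − λ(9/14).

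For methylene blue, λ = 0.373/0.357 = 1.045 and the responder SD is 0.54.

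| p | z(p) | λ(p) | Responder SD | True difference | Responder-only difference | Share kept |
|---|---|---|---|---|---|---|
| 20% | −0.842 | 0.350 | 0.76 | 1.208 | 1.208 + 0.350 − 1.045 = 0.513 | 42% |
| 30% | −0.524 | 0.497 | 0.70 | 0.891 | 0.891 + 0.497 − 1.045 = 0.343 | 38% |
| 50% | 0 | 0.798 | 0.60 | 0.366 | 0.366 + 0.798 − 1.045 = 0.119 | 33% |

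With methylene blue failure at 35.1% the shares kept are 52%, 47% and 41%; at 87.2% they are 35%, 31% and 26%. If both drugs fail equally often, the contrast is unbiased in this model, but each arm's mean is still too high.

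**Interval behaviour.** With all treated patients the 95% half-width is t(18) × √(2/10) = 2.101 × 0.447 = 0.94 SD, with 95% coverage. Simulation (100,000 trials per row) of the responder-only comparison gives:

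| p | Coverage, failures excluded, not replaced | Half-width | Coverage, all failures replaced (10 v 10) | Half-width |
|---|---|---|---|---|
| 20% | 71% | about 1.0 SD | 39% | 0.61 SD |
| 30% | 78% | about 1.0 SD | 53% | 0.58 SD |
| 50% | 91% | about 1.0 SD | 84% | 0.53 SD |

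Without replacement, about 8% to 9% of trials had fewer than two responders in an arm and gave no interval; they are left out.

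**Effect on the next trial.** Required size is proportional to variance/difference². Averaging the two responder variances gives (0.54² + 0.76²)/2 = 0.44, and likewise 0.39 and 0.33, where the true value is 1. A planner who fixed the target difference independently and borrowed only this SD would plan 44%, 39% or 33% of the size needed. One who borrowed both would plan (0.44/0.513²) ÷ (1/1.208²) = 2.4 times the size needed, and 2.6 and 3.1 times in the other two rows. The error can go either way.

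**The case against.** The best defence is that this is a declared descriptive pilot and that section 7.3, the statistical section, already names the right population. That supports the remedy but does not remove the conflict: section 3.1 is equally current and uses the word comparison, and no separate comparison is defined to which its exclusion could apply instead.

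Several stronger readings are tempting, and the protocol does not support them:

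- *That section 7.3 cannot be carried out, because section 4.4.1 collects no data on withdrawn subjects.* That sentence may mean no further data. Section 4.4.2 speaks only of not contacting the participant again, section 9.1 keeps data collected before authorization is revoked, and haemodynamics are recorded in the EHR as routine care. Section 4.4.1 also affects non-responders only if the investigator withdraws them. The wording is ambiguous, not unworkable.
- *That both drugs must look effective by construction.* This needs persistence to be judged by SVR below 500, which section 3.1 implies but does not state for the 30-minute check. It concerns SVR only; nothing comparable follows for blood pressure or vasopressor amount.
- *That the interval would be too narrow.* This requires failures to be replaced, which only section 4.4.1 permits. Under section 3.1 alone, responders vary less but are fewer, and the interval is no narrower than with all treated patients.
- *That failures go unreported.* Section 3.1 says their frequency may be used. What is missing is a commitment and an interval.
- *That the absence of a test, of power or of a stated between-arm interval is itself a serious defect.* In a descriptive pilot it is not. If summaries are given by arm, a reader can derive the unadjusted difference and interval.

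**Conclusion.** The point holds. Sections 3.1 and 7.3 give incompatible populations for the comparison, and section 4.4.1 adds to the conflict. Following section 3.1, or replacing failures under section 4.4.1, selects on the outcome.

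Under the illustration's assumptions only about a third to two-fifths of the true difference would be seen (26% to 52% over the exact interval for 9/14). The bias is always toward no difference in this model and vanishes when failure rates are equal. The coverage figures of 39%, 53% and 84% are the worst case and apply only with full replacement. The sizes depend on the Normal model, on a historical failure rate measured differently, and on assumed hydroxocobalamin rates. The contradiction depends on none of these. The change should be made before the data are analysed; the lack of a stated between-arm interval is secondary.

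**What to change.** Reconcile sections 3.1, 4.4.1 and 7.3 as follows:

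1. The comparison uses all treated patients in their randomized arm, including those still vasoplegic at 30 minutes.
2. Data already collected are kept, and EHR collection continues after treatment failure. Where authorization is revoked, section 9.1 governs.
3. Treatment failures are not replaced.
4. The failure rate is reported by arm with an exact 95% CI, as a commitment.
5. Any analysis without failures, including the section 7.3 sensitivity analysis where failures count as withdrawals, is labelled as selected on outcome.
6. The assigned-drug comparison uses haemodynamic values taken before any second drug.

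Secondary, in section 7.2: report the between-arm difference with a 95% CI for each measure, without a hypothesis test, and say that 10 per arm gives a half-width of about 0.94 SD. Baseline adjustment is optional. Any robust estimator for vasopressor amount should be fixed in advance, not chosen after a skewness check.

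The cost is a short paragraph in section 7.2 and a sentence or so in each of sections 3.1, 4.4.1 and 7.3. No new measurement is needed, since section 9.3 draws all data from the EHR, and not replacing failures needs fewer patients. The price is a less favourable apparent response in each arm. Postoperative outcomes will include patients who received both drugs and must be read as the result of starting with the assigned drug. Only data handling changes; rescue practice is untouched.

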SOP Standard Operating Procedure	SOP	Standard Operating Procedure			
SSRI Selective Serotonin Reuptake Inhibitor	SSRI	Selective Serotonin Reuptake Inhibitor			
SVR Systemic Vascular Resistance		Systemic Vascular Resistance			
VS Vasoplegic Syndrome		Vasoplegic Syndrome			
UPIRTSO Unanticipated Problems Involving Risk to Subjects or Others	UPIRTSO	Unanticipated Problems Involving Risk to Subjects or Others			

Study Summary

Title	The Efficacy of Intravenous Hydroxocobalamin versus Methylene Blue as Treatment for Intraoperative Vasoplegic Syndrome in Liver Transplant Patients	
Running Title	Methylene Blue vs Cyanokit	
Protocol Number	18-006247	
Phase n/a		
Methodology Randomized, Open-Label		
Overall Study Duration	12 months	
Subject Participation Duration	Less than 12 hours	
Single or Multi-Site	Single Center	
Objectives	The primary aim of this study is to describe the efficacy of hydroxocobalamin vs methylene blue	
Number of Subjects	20	
Diagnosis and Main Inclusion Criteria	Patients undergoing liver transplant surgery and experiencing vasoplegia intraoperatively	
Study Product, Dose, Route, Regimen	Hydroxocobalamin (Cyanokit): 5g IV infusion over 15 minutes	
Duration of Administration	Single dose intraoperatively	
Reference therapy	Methylene blue (PROVAYBLUE TM), 2 mg/kg IV bolus administered over 15 minutes	
Statistical Methodology	This pilot study is meant to be descriptive and it aims to collect basic data for future larger study	

1 Introduction

This document is a protocol for a human research study. This study will be carried out in accordance with the applicable United States government regulations and Mayo Clinic research policies and procedures.

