3.4 Primary Study Endpoints

The primary endpoint of the study will be the improvement in hemodynamic values as measured by SVR, systemic blood pressure, and amount of vasopressors administered. The monitoring and documentation of hemodynamic values is part of SOC practice during LT surgery.

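### With 10 patients per arm, the drug comparison needs each patient's pre-dose value, but Section 7.2 plans raw summaries only

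*Combined protocol and SAP*

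**What the plan says.** - **Objective.** Section 2 is comparative: "To assess the efficacy of hydroxocobalamin as compared to methylene blue on improving hemodynamic stability".
- **Endpoint.** Section 3.4 defines it as "improvement in hemodynamic values as measured by SVR, systemic blood pressure, and amount of vasopressors administered". It names no pre-dose reading, no post-dose reading and no formula for improvement.
- **Size and allocation.** Section 3.1 plans "10 patients in each group". Section 5.3 says that REDCap performs the randomisation and mentions no stratification factor.
- **Analysis.** For continuous data, Section 7.2 states "Continuous variables will be summarized using the sample mean, median, standard deviation, interquartile range, and range". It names no covariate, between-arm estimate or confidence interval, and does not say that the summaries are by arm.
- **Declared purpose.** The Study Summary says "This pilot study is meant to be descriptive and it aims to collect basic data for future larger study". Section 7.1 says that existing information on changes in the three measures is such that they "are not sufficient for sample size calculation", and wants data from which later power can be obtained.
- **Availability of data.** Section 3.4 notes that "The monitoring and documentation of hemodynamic values is part of SOC practice during LT surgery". Section 4.1 requires an SVR reading below 500 before dosing.
- **Who is compared.** Section 7.3 analyses everyone who received study drug. Section 3.1 removes from the comparison those still vasoplegic 30 minutes after dosing.

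**The concern.** Readers will set the two arms side by side and take the difference in improvement as the first estimate of relative effect. With 10 patients per arm and nothing in the stated design or analysis to handle pre-dose state, part of that difference may be a chance difference in how ill the arms were at dosing.

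The plan also leaves open whether post-dose values or changes are compared. The same imbalance affects these two differently and can push them in opposite directions. The estimate, and the variability figures that Section 7.1 wants for a future trial, would then depend on an unstated choice.

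**Working it through.** The plan has no sample size or precision figure to reproduce.

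**Inputs.** n = 10 per arm (Section 3.1), no stratification on pre-dose state (none stated in Section 5.3). The pre/post correlation r and the ratio k = post-dose SD / pre-dose SD are not in the documents, so they are assumed and varied. The model is linear with one slope, r × k, in both arms.

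**Step 1: size of chance imbalance.** In pre-dose SD units, the difference in arm means has SD √(2/10) = 0.447. Under a normal approximation, P(|difference| > 0.5) = P(|Z| > 0.5/0.447) = 0.264. For thresholds of 0.25, 0.75 and 1 SD the probabilities are 58%, 9% and 2.5%. These apply to each measure separately.

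**Step 2: how an imbalance D carries through.** Post-dose comparison: r × k × D. Change-score comparison: (r × k − 1) × D. Adjusted comparison: 0 on average.

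**Step 3: variance factors** (pre-dose variance = 1). Post-dose k²; change 1 + k² − 2rk; adjusted k²(1 − r²)(1 + 1/16), where 16 = 20 − 4.

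Equal SDs (k = 1), with D = 0.5 SD:

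| r | shift, post-dose | shift, change | variance, post-dose | variance, change | variance, adjusted |
|---|---|---|---|---|---|
| 0.2 | +0.10 | −0.40 | 1.00 | 1.60 | 1.02 |
| 0.5 | +0.25 | −0.25 | 1.00 | 1.00 | 0.797 |
| 0.8 | +0.40 | −0.10 | 1.00 | 0.40 | 0.382 |

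Multiplying by 2/10 and taking the root gives adjusted standard errors of 0.452, 0.399 and 0.277 SD. The change score gives 0.566, 0.447 and 0.283, and the post-dose value 0.447 throughout. In 100,000 simulated trials at each r, the correlation of the estimate with the imbalance was 0.00 for the adjusted estimate, 0.20 / 0.50 / 0.80 for post-dose values and −0.63 / −0.50 / −0.32 for change scores.

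**Step 4: SVR.** The entry limit of 500 narrows the pre-dose spread, so k may exceed 1. With k = 2 (assumed) and D = 0.5 pre-dose SD:

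| r | slope r × k | shift, change | variance, change | variance, adjusted | adjusted vs change |
|---|---|---|---|---|---|
| 0.2 | 0.4 | −0.30 | 4.20 | 4.08 | 3% lower |
| 0.3 | 0.6 | −0.20 | 3.80 | 3.87 | 2% higher |
| 0.5 | 1.0 | 0 | 3.00 | 3.19 | 6% higher |
| 0.7 | 1.4 | +0.20 | 2.20 | 2.17 | 1.5% lower |

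A change score over-corrects below a slope of 1, is exact at 1 and under-corrects above 1. The imbalance in absolute units may also be small for SVR. If pre-dose SVR were uniform over a range of 100 to 300 units (assumed), the SD of the arm difference would be (range/√12) × 0.447, or about 13 to 39 units.

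**Step 5: if Section 3.1's exclusion applied.** Section 1.3 reports that 9 of 14 patients responded inadequately to methylene blue. If that rate recurred (an assumption, since its definition differs from Section 3.1's), 10 × 5/14, or about 3.6, methylene blue patients would remain. With N patients left, the penalty 1/(N − 4) rises from 1/16 at 20 to 1/10 at 14 and 1/4 at 8.

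**The case against.** The strongest reply is that this is a declared descriptive pilot, with no test, alpha or power to distort. At 10 per arm, 80% power needs a difference near 1.25 SD (two-sided 0.05, assumed), so shifts of 0.1 to 0.4 SD would seldom decide anything. The correlation and residual SD could also be computed later from the same data. This limits the severity. It does not remove the point, because the objective is comparative and the estimate is meant to inform a larger trial.

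Four stronger readings are tempting, and the documents do not support them:

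- **Entry at an extreme SVR biases the drug comparison.** Drift back from a value below 500 is common to both randomised arms and cancels on average. What remains is imbalance in the realised sample, plus lost precision.
- **A change score always over-corrects.** Step 4 shows that this depends on the slope.
- **The plan ignores baseline.** Improvement in Section 3.4 and changes in Section 7.1 imply some pre/post comparison. The plan does not say which.
- **Adjustment always narrows the estimate.** At r = 0.2 it costs 2% against post-dose values, and for SVR it may gain nothing over a change score.

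Two practical objections also stand. The adjusted model needs a named post-dose reading, which the protocol lacks. And while pre-dose SVR must be read for eligibility, a retrievable pre-dose vasopressor amount is plausible rather than established.

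**Conclusion.** The point holds as an improvement worth making, not as a flaw that invalidates the plan. For each measure there is about a one in four chance that the arms' pre-dose means differ by more than 0.5 SD. With equal SDs, an imbalance of exactly 0.5 SD moves an unadjusted comparison by 0.1 to 0.4 SD over correlations of 0.2 to 0.8. The unadjusted difference remains unbiased over repeated randomisations.

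The 26% rests only on 10 per arm, randomisation not stratified on pre-dose state and approximate normality of the mean difference. The shifts and variance gains also rest on assumed correlations and SD ratios. That the summaries in Section 7.2 are by arm is an inference from the comparative objective.

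**What to change.** In Section 7.2, beside the descriptive table:

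1. Tabulate pre-dose SVR, blood pressure and vasopressor amount by arm.
2. Name one pre-dose and one post-dose reading or window. Measure vasopressor amount the same way in both, and confirm that the pre-dose amount can be retrieved.
3. For each measure, report the arm difference with a confidence interval, labelled exploratory, from a linear model with arm and that measure's pre-dose value (log scale if skewed).
4. Report the pre/post correlation and residual SD for planning the future trial.
5. Run this in all treated patients, as in Section 7.3, and reconcile that with the exclusion in Section 3.1 of patients still vasoplegic at 30 minutes. Section 4.4.1 needs the same reconciliation, since it lists treatment failure as a reason for withdrawal and says that no data are collected after withdrawal or for withdrawn patients. Baseline adjustment does not repair selection on outcome.

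The cost is a short addition to Section 7.2, the definitions in item 2, the reconciliation in item 5, and three small models at one degree of freedom each.
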